#### **10.6.5 ECOG Performance Status**

ECOG performance status scores will be summarized for each treatment cohort using shift table. The shifts in scores from baseline to worst ECOG score on treatment will be summarized.

### **10.7 Efficacy Analyses**

All efficacy analysis will be performed using the safety analysis set. The analysis of DOR will only include subjects who have achieved objective response.

### **10.7.1 Best Overall Response, Disease Control Rate and Overall Response Rate per RANO criteria**

Measurable disease (bidimensional) as defined by the RANO criteria. RANO criteria (Wen 2010) will be followed for selection of measurable and non-measurable lesions and about the number of lesions to be assessed, as well as for the assessments of response and progression.

Disease Control Rate (DCR) is defined as the proportion of subjects who achieve a best response of SD, PR or CR at any point of the study.

Overall response Rate (ORR) is defined as the proportion of subjects who achieve a best response of PR or CR at any point of the study.

The primary analysis of DCR and ORR will be conducted using safety analysis set. DCR and ORR will be calculated with the corresponding exact binomial 2-sided 95% CI and 1-sided 90% CI (or 2-sided 80% CI) for treatment cohort.

### **10.7.2 Duration of Response per RANO criteria**

The DOR is defined as the interval from the first documentation of response to the earlier of the first documentation of definitive disease progression or death from any cause. The DOR will be summarized appropriately for subjects in safety analysis set who achieved response (CR or PR) at any point of the study. Kaplan-Meier methods will be used to estimate event-free curves and corresponding quantiles (including the median).

Data from surviving, non-progressing subjects will be censored at the date of the last adequate disease assessment that is on or before the start date of the new antitumor therapy. Data from subjects who have disease progression or die after more than one missed visit will be censored at the last visit date before the missing assessments which lack objective disease assessment. The details of definition of progression events and censoring rules are the same as for PFS endpoint and are listed in [Appendix 12.3](#)

### **10.7.3 Progression-free Survival Per RANO criteria**

Progression-free survival is defined as the interval from the start of therapy to the earlier of the first documentation of objective disease progression or death from any cause,

whichever occurs first. Kaplan-Meier (K-M) methods will be used to estimate the event-free curves and corresponding quantiles (including the median).

Data from surviving, non-progressing subjects will be censored at the date of the last adequate disease assessment that is on or before the start date of the new antitumor therapy. Data from subjects who have disease progression or die after more than one missed visit will be censored at the last visit date prior to the missing assessments which lack objective disease assessment. The details of definition of progression events and censoring rules are listed in [Appendix 12.3](#).

In the primary analysis using safety analysis set, study treatment end date will be used as the date of progression for subjects who discontinued study treatment due to disease progression or death prior to 1st radiographic assessment. Data for subjects who discontinued study treatment prior to 1st radiographic assessment due to reasons other than disease progression or death will be censored at their study treatment start date.

#### **6-month Progression-free Survival (PFS-6) Rates and 4-month Progression-free Survival (PFS-4) Rates**

PFS-6 rate is defined as the K-M estimate of subjects alive and without documented disease progression at 6 months. The K-M method will be used to estimate the PFS-6 rate and corresponding exact 2-sided 95% CIs. The same method applies to the PFS-4 rate.

#### **10.7.4 Overall Survival**

Overall survival is defined as the time from date of enrollment until date of death due to any cause. Subjects who are known to be alive or whose survival status is unknown will be censored at the date last known to be alive. Subjects who lost to follow-up for survival immediately after randomization will be censored at first dose date.

OS will be summarized for safety analysis set. The analysis methods for OS will be similar to those described for progression-free survival. Censoring rules are defined in more detail in [Appendix 12.4](#).

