3.3.4 Enrollment Procedures

- Enrollment of a subject into the study will be performed according to the following procedure: The study center will notify the sponsor when a clinically eligible subject is identified and is ready to screen, to ensure enrollment availability on the study.
- After the subject has signed and dated the Informed Consent Form (ICF), all screening procedures have been completed, and eligibility has been confirmed, the subject can be officially enrolled into the study.
- To confirm eligibility the study center will fax/email a completed Enrollment Confirmation Form to the sponsor. The enrollment date will be the date that the Sponsor confirms enrollment.
- The sponsor will aim to fax/email a completed Enrollment Confirmation Form to the study center within 24 hours.

Treatment must begin within the screening window ([Section 4.1](#)).

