3.4.3 Administration of Study Drug

Investigators are prohibited from supplying acalabrutinib to any subjects not properly enrolled in this study. The investigator must ensure that subjects receive acalabrutinib only from personnel who fully understand the procedures for administering the drug.

Acalabrutinib is intended to be administered orally twice daily for those in the 200-mg BID cohort and once daily for those in the 400-mg QD cohort, with 8 ounces (approximately 240 mL) of water. For subjects receiving acalabrutinib 200 mg BID, doses should be administered 12 hours apart (a window of ± 1 hour is allowed). The capsules should be swallowed intact. Subjects should not attempt to open capsules or dissolve them in water. Note: Under Amendment 2 of the protocol, the SAC observed that the response and disease-control rate noted in the 200-mg BID cohort were numerically higher than in the 400-mg QD cohort. Therefore, the 400-mg QD cohort was discontinued.

If a dose is not taken within the allowed window, it can be taken up to 3 hours after the scheduled time with a return to the normal schedule the same or following day. If it has been >3 hours, the dose should not be taken, and the subject should take the next dose at the next scheduled time. The missed dose will not be made up and must be returned to the site at the next scheduled visit.

Guidance on coadministration of acalabrutinib with agents that affect gastric pH is provided in [Section 3.9.6](#).

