4.1.5 Confirmation of Eligibility

Subject eligibility for enrollment will be assessed per [Section 3.3](#). All screening procedures, unless otherwise indicated, should be completed within 21 days of the first dose of study drug.

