5.4.4 Analysis of Efficacy Parameters

Response Rate

ORR is defined as the proportion of subjects who achieve a CR or partial response (remission) (see [Section 4.2](#)). ORR will be calculated, and the corresponding 2-sided exact 95% CI will be derived.

Duration of Response

For subjects who achieve objective response, DOR is defined as the time from the first tumor assessment showing response to the time of confirmed disease progression or death due to any cause, whichever occurs first. Subjects who are still alive and free from progression at the time of data cutoff date, are lost to follow-up, have discontinued from the study, or have initiated other non-protocol antitumor therapy (NPT) will be

censored at the last evaluable tumor assessment. A Kaplan-Meier (K-M) curve will be presented for DOR and K-M median will be calculated with 2-sided 95% CI.

Progression-Free Survival

PFS is defined as the time from first dose to documented disease progression, or death from any cause, whichever occurs first. Subjects who are still alive and free from progression at the time of data cutoff date, are lost to follow-up, have discontinued from the study, or have initiated NPT will have their PFS time censored at last evaluable assessment (or, if there is no post-baseline tumor assessment, at the time of first dose). A K-M curve will be presented, and K-M estimates as well as exact 2-sided 95% CIs will be calculated for event time quartiles, and event-free rates at the protocol-specified disease assessment times.

6-month and [CCI] Progression-Free Survival Rates

PFS-6 rate is defined as the K-M estimate of subjects alive and without documented disease progression at 6 months. In this study, 1 month is defined as 30.4375 days. The K-M method will be used to estimate the PFS-6 rate and corresponding 95% CIs.

[CCI]

Overall Survival

Overall survival (OS) is defined as the time from first dose to death from any cause. Subjects who are still alive at the time of data cutoff date, are lost to follow-up, or have discontinued from the study will have their OS time censored at the last date known to be alive on or before the data cutoff date. The analysis of OS will be conducted, where applicable, using the same analysis method described for PFS.

The SAP will describe analyses of all other exploratory endpoints.

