## **6 ANALYSIS SETS**

### **6.1 Safety Analysis Set**

All efficacy and safety analysis will be performed using the safety population, which consists of all subjects who receive any amount of acalabrutinib. The analysis of DOR will only include subjects who have achieved objective response.

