### **10.2 Subject Accountability**

The number of subjects enrolled by site, country and region (US and ex-US) will be presented. Subject disposition will be summarized for all enrolled subjects including the following information:

- Proportion of subjects who received study drug
- Proportion of subjects with study drug discontinuation and primary reason for study drug discontinuation
- Proportion of subjects discontinuing study and reasons for study discontinuation
- Time on study

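### The SAP starts overall survival at enrollment while the protocol starts it at first dose, adding up to about 21 event-free days per subject

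*SAP*

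**What the plan says.** SAP 10.7.4: "Overall survival is defined as the time from date of enrollment until date of death due to any cause".

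Protocol 5.4.4: "Overall survival (OS) is defined as the time from first dose to death from any cause".

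The protocol makes these separate dates. Section 3.3.4 fixes enrollment: "The enrollment date will be the date that the Sponsor confirms enrollment". That confirmation comes after screening is complete. Section 3.4.3 rules out earlier dosing: "Investigators are prohibited from supplying acalabrutinib to any subjects not properly enrolled in this study". Section 3.3.4 also limits the delay: "Treatment must begin within the screening window". Section 4.1.5 sets the window, stating that screening procedures "should be completed within 21 days of the first dose of study drug". The SAP itself separates the two steps, because its disposition table for enrolled subjects (10.2) includes "Proportion of subjects who received study drug".

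OS is summarised in the safety set, "which consists of all subjects who receive any amount of acalabrutinib" (SAP 6.1).

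Elsewhere the SAP works from first dose. PFS (10.7.3) starts at the start of therapy, and Study Day 1 (12.1) is the first-dose date.

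**The concern.** One secondary endpoint has two time origins. A programmer who follows SAP 10.7.4 literally will produce OS times that do not meet the definition in the supplied protocol.

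The extra time is also of a particular kind. Every subject in the OS analysis received drug, so every one was alive at first dose. The interval from enrollment to first dose is therefore event-free by construction, and it lies before any treatment.

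PFS and OS would then appear in the same report on different clocks. A subject who dies without documented progression, with the death counted as a PFS event, would have an OS time longer than the PFS time although the same death ends both.

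**Working it through.** The documents give no OS figure to reproduce, so the check is a bound followed by an illustration.

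**Bound on the gap.** From protocol 3.3.4, 3.4.3 and 4.1.5: last screening procedure ≤ enrollment ≤ first dose, and first dose follows screening by at most 21 days. Hence 0 ≤ gap ≤ 21 days. At the SAP's 30.4375 days per month, the ceiling is 21 / 30.4375 = 0.69 months. Reaching it needs all screening and the sponsor's confirmation to be complete on Day −21, which is unlikely. Same-day dosing gives zero.

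**A constant gap.** If every subject had the same gap, the Kaplan-Meier curve would move right by exactly that gap. At the ceiling the median rises by 0.69 months, which is 0.69 / 6 = 11.5% of an assumed 6-month median or 0.69 / 9 = 7.7% of an assumed 9-month median. A 7-day gap adds 7 / 30.4375 = 0.23 months.

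**Variable gaps.** Assumptions: exponential OS from first dose with median 6 or 9 months; n = 15 or 9, the cohort sizes in SAP Table 1; an independent uniform gap per subject; 20,000 simulated trials per setting. The Kaplan-Meier median was computed with and without the gap.

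| Gap range (days) | Mean gap (months) | Mean rise in median, no censoring (months) | Mean rise, censoring uniform over 3–18 months (months) |
|---|---|---|---|
| 0–3 | 1.5 / 30.4375 = 0.049 | 0.049–0.050 | 0.048–0.052 |
| 0–7 | 3.5 / 30.4375 = 0.115 | 0.115–0.116 | 0.112–0.116 |
| 0–14 | 7 / 30.4375 = 0.230 | 0.230–0.231 | 0.229–0.233 |
| 0–21 | 10.5 / 30.4375 = 0.345 | 0.344–0.349 | 0.348–0.353 |

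The average rise is simply the mean gap. Even for 0–21 days it is under 6% of a 6-month median and under 4% of a 9-month median.

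**Direction.** Without censoring the median never fell. With censoring it fell in 0.1% to 1.3% of the simulated trials that had an estimable median, because unequal gaps can reorder events and censorings. For example, take an event at day 9 and censorings at days 10 and 20: survival after the event is 2/3. A 2-day gap for the first subject alone moves the event to day 11, after the first censoring, and survival drops to 1/2.

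**Comparison with sampling error.** For exponential data with all deaths observed, the standard error of the log sample median is 1 / (ln 2 × √n): 0.373 for n = 15 and 0.481 for n = 9. Around a 6-month median, 6 × exp(±1.96 × SE) gives 2.9–12.5 and 2.3–15.4 months. The exact 2.5%–97.5% ranges of the middle order statistic are 2.7–11.5 and 2.1–13.4 months.

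**The case against.** - **Not a selection effect.** SAP 3.2 and Table 1 show 15 subjects enrolled and 15 treated at 200 mg BID, and 1 + 8 = 9 enrolled and 9 treated at 400 mg QD. All 24 enrolled subjects were dosed, so nobody is excluded by analysing only dosed subjects. This stands. The issue is a mismatch of origin; the pre-dose interval is still event-free for everyone analysed.
- **Protocol version.** The SAP is written to protocol Amendment 2.0 of 21 March 2017. The supplied protocol is later: its Appendix 3 cites web pages accessed in July 2018. The Amendment 2.0 wording for OS cannot be checked, so a departure from the version the SAP implements is not shown. This also stands. The mismatch with the supplied protocol, and with the SAP's own PFS and study-day origins, does not depend on it.
- **The SAP may already imply first dose.** Section 10.1 bases time-to-event calculations on study day, 12.1 sets Day 1 at first dose, and 10.7.4 says its methods resemble those for PFS. A programmer might therefore use first dose. But 10.1 mainly contrasts dates with visit labels, and a general rule does not clearly override an explicit definition. Appendix 12.4 lists event and censoring dates, not an origin.
- **No consequence.** OS is secondary and descriptive, SAP section 5 tests no hypothesis, both cohorts share the origin, and Phase 2 was not opened. All true, and this is why the point is minor.
- **The 21 days is soft.** The screening window is worded as a recommendation with exceptions, and the ceiling is unlikely to be reached. It should be read as an approximate bound, not an expected gap.

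**Conclusion.** The inconsistency is real. As written, SAP 10.7.4 gives OS times that differ from the supplied protocol's definition by the enrollment-to-dose gap, and that are not on the same clock as PFS. Severity is minor.

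The size is 0 to about 0.69 months per subject. The average rise in the median is about 0.05 to 0.35 months under the assumed uniform gaps, almost always upward. These averages rest on assumed gap distributions and, for the simulation, on exponential survival and the assumed censoring pattern; the bound rests only on the protocol's own rules. The shift is small against the uncertainty of a median from 15 or 9 subjects, and no decision rule is affected. It is nevertheless systematic and easily removed.

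**What to change.** In SAP 10.7.4, define OS as the time from the first dose of acalabrutinib to death from any cause. This matches protocol 5.4.4 and the PFS origin in SAP 10.7.3.

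In the same section, the rule for subjects lost to follow-up at once refers to randomization. Change this to first dose, as in Appendix 12.4. Both versions censor at the first-dose date, so this edit changes no number.

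The cost is two wording edits and one derivation. If the SAP is already final, its section 1 requires the change to be documented in the clinical study report. The only downside is that reported OS may be slightly shorter.

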#### **10.7.5 Pharmacokinetic, Pharmacodynamic and Biomarker Analyses**

Additional pharmacodynamic, pharmacokinetic and biomarker analyses may be performed, as deemed appropriate. A separate analysis plan for these analyses will be developed by PK/PD group at Acerta.

## 12 APPENDICES

### 12.1 Definitions

#### Study Day

The study day will be calculated in reference to the first dose date of study drug. Study Day 1 is defined as the first dose date of study drug. For assessments that occur on or after the first dose date of study drug, study day is defined as (date of assessment – first dose date of study drug + 1). For assessments that occur prior to the first dose date of study drug, study day is defined as (date of assessment – first dose date of study drug). There is no Study Day 0.

#### Duration of Exposure

The duration of exposure to acalabrutinib will be calculated in months as (last dose date - first dose date + 1) / 30.4375. The gaps in treatment will be included. The duration of exposure in days will be used for planned dose calculation.

#### Total Dose

Total dose received is a sum of all actual doses taken through the treatment duration and will be presented in grams. For scheduled drug administration visits that are skipped the actual dose will be 0.

#### Average Daily Dose

Average daily dose is total dose divided by duration of exposure in days.

#### Relative Dose Intensity

Relative dose intensity is the ratio of total dose to the protocol-specified total dose through the duration of exposure.

## **12.2 Imputation rules for partial or missing dates**

Imputation of partial dates will be made for AE onset and stop dates, start and end dates of concomitant medication, start date of subsequent anticancer therapy, date of initial diagnosis and death date. If dates are completely missing, no imputation will be made. For any partial date with missing year, no imputation will be made.

The general rule for imputation is:

- If only day is missing, then the 15th of the month will be used.
- If only year is present, then June 30th will be used.

If such imputation date for initial diagnosis is on or after date of first dose, then date of first dose – 1 will be used. If such imputed date for subsequent anticancer therapies is before date of last dose, then date of last dose + 1 will be used.

If the imputed date is for an AE start date and is in the same year and month as but before the first dose date, then the first dose date will be used, or if the imputed AE start date is after the AE end date, then the AE end date will be used. If the imputed date is for an AE start date and is in the same year and month as but after the last dose date + 30 days, then the last dose date + 30 days will be used.

If the imputed date is for an AE end date and is after the death date, then the death date will be used, or if the imputed AE end date is before the AE start date, then the AE start date will be used.

Every effort will be made to obtain complete dates for deaths. If both month and day are missing for death date or a death date is totally missing, do not impute and censor the subject survival time. If death year and month are available but day is missing, the following algorithm will be used:

- If mmyyyy for last contact date = mmyyyy for death date, set death date to the day after the last contact date.
- If mmyyyy for last contact date < mmyyyy for death date, set death date to the first day of the death month.
- If mmyyyy for last contact date > mmyyyy for death date, data error and do not impute.

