5.3 MISSING DATA HANDLING

No imputation of values for missing data will be performed except that missing or partial start and end dates for AEs and concomitant medication will be imputed according to prespecified, conservative imputation rules. Subjects lost to follow-up (or drop out) will be included in statistical analyses to the point of their last evaluation.

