### **10.6.1 Adverse Events**

The Medical Dictionary for Regulatory Activities (MedDRA v20.1 or later) will be used to code all AEs to a system organ class and a preferred term. The severity of the AE will be assessed by National Cancer Institute (NCI) Common Terminology Criteria for Adverse Events (CTCAE) Version 4.03. Study drug-related AEs are those assessed by investigator as related.

All AE tables will be summarized by treatment cohort.

TEAEs are defined as those events that occur or worsen on or after the first dose of study drug (acalabrutinib), through the treatment phase, and within 30 days following the last dose of acalabrutinib.

TEAEs will be summarized by system organ class (SOC) and preferred terms (PTs) as well as preferred terms only in descending order of frequency, by CTCAE severity grade.

Drug-related TEAEs, treatment-emergent serious adverse events (TESAEs), TEAEs leading to study drug discontinuation or dose modifications or dose delay will be summarized by PTs in descending order of frequency and by CTCAE severity grade.

Death information is reported in the study exit case report form (CRF) and death information CRF for all deaths. Incidences of deaths are to be reported, along with the primary cause of death.

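### An AE onset known only by year is set to June 30, and the first-dose safeguard can never act on that date, so some on-treatment AEs are dated before first dose and leave the TEAE tables

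*SAP*

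**What the plan says.** SAP 12.2 has two general rules for partial dates: "If only day is missing, then the 15" of the month, and "If only year is present, then June 30". Three adjustments then apply to an imputed AE start:

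- First-dose safeguard: if the imputed date "is in the same year and month as but before the first dose date, then the first dose date will be used".
- End-date cap: "if the imputed AE start date is after the AE end date, then the AE end date will be used".
- Last-dose safeguard: if the imputed date "is in the same year and month as but after the last dose date + 30 days", it is moved back to that limit.

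SAP 10.6.1 sets the window to which these dates are compared: "TEAEs are defined as those events that occur or worsen on or after the first dose of study drug", up to 30 days after the last dose. Protocol 5.4.1 restricts the AE summaries to treatment-emergent events. Protocol 5.3 says AE dates are imputed "according to prespecified, conservative imputation rules", and SAP 9 repeats that standard and points to Appendix 12.2 for the details.

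**The concern.** The two same-month safeguards suit the day-missing case. With the 15th of a known month, any month that overlaps the window either lies inside it or is the month of one of its limits, where the safeguard acts. They do not carry over to the year-only case, where June 30 may be months away from the true onset and from both limits of the window.

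The error goes one way: an event that truly began on treatment is dated outside the window and is not summarised. Safety is one of the two primary objectives, and the cohorts have 15 and 9 subjects. One subject lost from an incidence row moves it by 1/15 = 6.7 or 1/9 = 11.1 percentage points.

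Two features suggest an oversight. In the same appendix, the adjustments for initial diagnosis and for subsequent therapy carry no same-month condition, so they do work for year-only dates. And Protocol 6.2.1 requires only SAEs to be reported between consent and first dose, so a non-serious AE in the database most likely began after first dose, which is where the rule may fail to put it.

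**Working it through.** The plan states no figure to reproduce. The inputs are the rules above. The documents give no dosing or AE dates, so the dates below are illustrative.

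**Step 1: when each adjustment can act on June 30.**

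- First-dose safeguard: it needs a first dose in June but later than June 30. There is no such day, so it never acts.
- Last-dose safeguard: it needs last dose + 30 days to fall in June and before June 30, that is June 1 to 29, or 29 of 365 days.
- End-date cap: it acts only when June 30 is later than the AE end date. It can pull a late date back but cannot push an early date forward.

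**Step 2: examples.**

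| First dose | Last dose | Last dose + 30 | Onset | AE end | Imputed start | TEAE? |
|---|---|---|---|---|---|---|
| 1 Sep 2016 | 23 Nov 2016 | 23 Dec 2016 | 2016 | 20 Oct 2016 | 30 Jun 2016 | No |
| 10 Jan 2017 | 3 Apr 2017 | 3 May 2017 | 2017 | ongoing | 30 Jun 2017 | No |
| 10 Jan 2017 | 3 Apr 2017 | 3 May 2017 | 2017 | 1 Mar 2017 | 1 Mar 2017 | Yes |
| 1 Feb 2017 | 20 May 2017 | 19 Jun 2017 | 2017 | ongoing | 19 Jun 2017 | Yes |

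Row 1 is the early-side failure, which no rule corrects. Row 2 is the late-side failure. Rows 3 and 4 show the end-date cap and the last-dose safeguard working.

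**Step 3: share lost, given a year-only onset.** Assume first dose uniform over a 365-day year and true onset uniform over the window of W = exposure + 30 days. There are 365 × W combinations.

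- Early loss: first dose falls on one of the 184 days from July 1 to December 31, and onset is in the same year. With r days left in the year (counting the first-dose day), min(r, W) onsets are lost. Share = Σ(r = 1 to 184) min(r, W) / (365W).
- Late loss with no end date: the window closes on one of the 151 days from January 1 to May 31, and onset is in that year. Share = Σ(j = 1 to 151) min(j, W) / (365W), with j the day of the year on which the window closes.

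| Exposure | W | Early | Late, no end date | Total, no end date |
|---|---|---|---|---|
| 60 d | 90 | 12,555/32,850 = 38.2% | 9,585/32,850 = 29.2% | 67.4% |
| 90 d | 120 | 14,940/43,800 = 34.1% | 10,980/43,800 = 25.1% | 59.2% |
| 180 d | 210 | 17,020/76,650 = 22.2% | 11,476/76,650 = 15.0% | 37.2% |

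**Step 4: with an AE end date 7 days after onset.** The early loss is unchanged. On the late side the cap moves the start to the end date. If that lies just past the window, the last-dose safeguard (applied after the cap) pulls it back unless it has crossed into the next month. A window closing m = 0 to 6 days before month end leaves 7 − m lost onsets, which sums to 28 per month, or 140 over January to May. The totals become:

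- 60 days: (12,555 + 140)/32,850 = 38.6%
- 90 days: (14,940 + 140)/43,800 = 34.4%
- 180 days: (17,020 + 140)/76,650 = 22.4%

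A day-by-day enumeration of the coded rules gives the same totals in both cases. Under the same assumptions with no end dates, the loss is 76% at 28 days of treatment and 20% at 365 days.

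**The case against.** The strongest reply is that this hardly ever arises. AEs are assessed at every evaluation, visits are weekly in Cycles 1 and 2 and at least once per cycle after that, and a new on-treatment event whose month is unknown should be rare. The analysis is descriptive: SAP 5 tests no hypothesis, and SAP 3.1 records that Phase 2 was not recommended. The word conservative is not defined in either document. The points about rarity and stakes stand and limit the importance of the finding. They do not make the rule right. Whatever else conservative means for a safety table, it does not fit with moving on-treatment events out of it.

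Three stronger readings are tempting, and the documents do not support them.

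- A reader might infer that all the safeguards fail. Only the first-dose safeguard is inoperative. The last-dose safeguard acts for windows closing June 1 to 29, and the end-date cap already in SAP 12.2 rescues late-side events that end inside the window.
- A reader might infer that every year-only AE is lost for subjects first dosed from July to December. An onset recorded in the following calendar year can be kept, for example when treatment runs past the next June 30 or when the AE end date lies in the window.
- A reader might take 67%, 59% and 37% as the expected loss. Those figures assume that no AE has an end date, whereas Protocol 6.2.2 asks for start and end dates. They are the upper end of a range.

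**Conclusion.** The defect holds. For a subject first dosed after June 30, a year-only onset in the first-dose year is always imputed to before first dose, and no rule in SAP 12.2 corrects it, even when the recorded end date is on treatment. On the late side, an ongoing AE, or one with no end date in the window, is lost when last dose + 30 days falls before June of the onset year. Neither result meets the conservative standard of Protocol 5.3 and SAP 9.

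Given a year-only onset, the loss at 60, 90 and 180 days of exposure lies between about 39%, 34% and 22% (end date 7 days after onset, almost all of it early-side) and 67%, 59% and 37% (no end dates). These figures rest on uniform first-dose dates and uniform onset, and neither assumption can be checked from the documents. They are conditional shares, not shares of all AEs. The number of year-only onsets is not given and is probably very small, so the likely effect on the tables is minor. The rule is still wrong as written and cheap to correct.

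**What to change.** Replace the June 30 rule for AE onset with one sentence in SAP 12.2: where only the year is known, use the first-dose date if it is the first-dose year, otherwise January 1 of that year. Keep the existing cap at the AE end date.

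This retains every truly on-treatment event. In the first-dose year the imputed date is first dose itself. In a later year, January 1 is after first dose and no later than the true onset. The end-date cap cannot move an on-treatment event to before first dose. The enumeration found 0% misclassified. A year before the first-dose year, or an end date before first dose, still gives a pre-dose event.

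The cost is that sentence and a small programming change. There are two downsides. A few events that truly began before first dose may be counted as treatment-emergent, though Protocol 6.2.1 limits required pre-dose reporting to SAEs. And onset is pulled to the earliest possible date, which shortens time to onset and lengthens duration. Both are listed safety characteristics in SAP 4.1, so flag these AEs as imputed in any onset or duration summary.
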